## AMENDMENT HISTORY

**Table 1: SAP Version History Summary**

SAP Version	Approval Date	Change	Rationale
1.0	27 September 2021	Not Applicable	Initial release
2.0	07 July 2022	1) the upper age limit was changed from less than 65 years to 75 years inclusive 2) mean and standard deviation was added for continues baseline variables 3) Methods for analyses of AESIs were added	To align with the CTP Amendment 2 To better see the differences between groups in baseline characteristics Algorithms to describe AESIs were specified

## 1. INTRODUCTION

This statistical analysis plan (SAP) contains information needed to perform the complete safety and immunogenicity analysis of the VAC18193RSV3004 trial. It applies to all the analyses described in Section 9.4 of the clinical trial protocol (CTP). The specifications of individual tables, listings, and figures to be generated in each analysis will be described in a separate data presentation specifications (DPS) document.

### 1.1. Objectives and Endpoints

Refer to Section 3 of the CTP. The statistical hypotheses are described in Section 2 of this document.

### 1.2. Study Design

Please refer to Section 4.1 of the CTP for more details on the study design, and Section 6.3 of the CTP for details on randomization and procedures for maintaining the blind.

## 2. STATISTICAL HYPOTHESES

To demonstrate non-inferiority in terms of humoral immune responses induced by vaccination with one dose of the Phase 3 CTM compared with one dose of the Phase 2b CTM, the following hypotheses will be tested:

#### *Null Hypothesis:*

The Phase 3 CTM induces inferior GMTs of the pre-F ELISA titers on Day 15, compared with the Phase 2b CTM.

#### *Alternative Hypothesis:*

The Phase 3 CTM induces non-inferior GMTs of the pre-F ELISA titers on Day 15, compared with the Phase 2b CTM.

Non-inferiority will be shown if the lower limit of the 2-sided 95% CI around the estimated GMR (Phase 3 CTM versus the Phase 2b CTM) lies entirely above 0.67.

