#### **9.2. Sample Size Determination**

Sample size calculations were performed under the following assumptions:

- no difference in the Day 15 pre-F ELISA between the Phase 3 CTM and the Phase 2b CTM (ie, assuming a true GMR of Day 15 pre-F ELISA titers equal to 1)
- a standard deviation of 1.3 at the  $\log_2$  scale for pre-F ELISA on Day 15a
- a non-inferiority margin of 0.67 (2/3)
- 2-sided  $\alpha$  of 5%

A total of 105 evaluable participants per group are needed to have 90% power to demonstrate non-inferiority.

---

a Based on Day 15 pre-F ELISA results obtained from Cohort 2, Group 14 in study VAC18193RSV1004.

To account for exclusions from the Per-protocol Immunogenicity (PPI) Set (see Section 9.3), drop-outs and missing samples, approximately 120 participants per group should be enrolled.

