#### **9.4.3. Immunogenicity Analyses**

##### **9.4.3.1. Primary Endpoint**

The primary immunogenicity objective will be assessed by calculating the 2-sided 95% CIs for the difference in log-transformed Day 15 pre-F ELISA titers (ie, Group 1 versus Group 2).

The CI will be calculated via an analysis of variance (ANOVA) including both groups with Day 15 pre-F ELISA titers as dependent variable and group as independent variable. The CIs around the difference will be back-transformed (by exponentiation) to CIs around a GMR (GMTPhase 3 CTM/GMTPhase 2b CTM) and compared to the non-inferiority limits of 0.67 (2/3).

Non-inferiority between the Phase 3 CTM versus the Phase 2b CTM is demonstrated if the lower limit of the 2-sided 95% CI of the estimated GMR lies entirely above 0.67.

As a sensitivity analysis to assess the impact of baseline titers, the primary endpoint will also be evaluated adjusting for the respective baseline titers. For immunogenicity, baseline is considered as the last assessment pre-vaccination. In a second sensitivity analysis, different variances between the groups will be allowed. Therefore, the CIs will be calculated via Welch's ANOVA.

Finally, pre-F ELISA titers will be summarized descriptively. For continuous parameters, descriptive statistics of the actual values (geometric mean and 95% CI) will be calculated at all timepoints. Additionally, geometric mean fold increases from baseline and corresponding 95% CIs will be calculated. Graphical representations of immunogenicity parameters will be created as applicable. For categorical variables, frequency tables will be presented.

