### **5.3.2. Analysis Methods**

The primary immunogenicity objective will be assessed by calculating the 2-sided 95% CIs for the difference in log-transformed Day 15 pre-F ELISA titers (ie, Group 1 versus Group 2).

The CI will be calculated via an analysis of variance (ANOVA) including both groups with Day 15 pre-F ELISA titers as dependent variable and group as independent variable. The CIs around the difference will be back-transformed (by exponentiation) to CIs around a GMR (GMTPhase 3 CTM/GMTPhase 2b CTM) and compared to the non-inferiority limits of 0.67 (2/3).

Non-inferiority between the Phase 3 CTM versus the Phase 2b CTM is demonstrated if the lower limit of the 2-sided 95% CI of the estimated GMR lies entirely above 0.67.

As a sensitivity analysis to assess the impact of baseline titers, the primary endpoint will also be evaluated adjusting for the respective baseline titers. For immunogenicity, baseline is considered as the last assessment pre-vaccination. In a second sensitivity analysis, different variances between the groups will be allowed. Therefore, the CIs will be calculated via Welch's ANOVA.

The significance level ( $\alpha$ ) is 5% (2-sided). As no interim analyses before the primary analysis are planned, no multiplicity adjustments are needed.

Pre-F ELISA titers will be summarized with descriptive statistics. Descriptive statistics (N, geometric mean§ and corresponding 95% CI) of the actual values will be calculated for continuous immunogenicity parameters at all timepoints. Geometric mean§ fold increases from baseline and corresponding 95% CIs might additionally be calculated. *§calculate the mean and corresponding 95%CI of the log2 transformed values, back-transform this mean [ie 2mean] and CI [ie 2CI].*

The tables will also show the fold increases together with the percentage of participants with a 2- and a 4 -fold increase from baseline.

Actual values and fold changes from baseline will also be presented in dot-plots with dots for participant values, and the corresponding geometric mean and 95% CI per timepoint. In addition, plots of GMT over time, combining the regimens in one graph (without individual participant dots) will be created. Reverse distribution curves of the actual values will be provided, for baseline and Day 15. In the graphs, original values will be displayed on the log2 scale.

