## **5.5. Safety Analyses**

Safety endpoints (secondary endpoints):

- Solicited local (injection site) and systemic AEs for 7 days after vaccination
- Unsolicited AEs for 28 days after vaccination
- SAEs and AESIs until 6 months after vaccination

Safety analyses will be performed on the FAS. Continuous variables will be summarized using the following statistics, as appropriate: number of observations, median, minimum and maximum. Frequencies and percentages (one decimal place) will be generated for categorical variables. No formal comparisons between groups will be provided.

Safety data will be analyzed by study intervention regimens as designed per protocol, per phase and also across the entire study period where applicable. For unsolicited AE, denominator for the percentages is the number of participants in the considered population and phase for a certain regimen (incidence per 100 participants/phase). For solicited AEs, the denominator for the percentages is the number of participants with data assessed by the investigator in the considered population and phase for a certain regimen (incidence per 100 participants/phase).

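### Does writing the non-inferiority limit as 0.67 in some places and as 0.67 (2/3) in others leave the primary decision rule open?

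*SAP*

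**What the plan says.** The success criterion is stated seven times: in the protocol synopsis (Hypotheses, and again under Immunogenicity Analyses), protocol sections 3, 9.1 and 9.4.3.1, and SAP sections 2 and 5.3.2. Each time the limit is 0.67 without a fraction. In SAP section 2, the lower limit of the CI must be one that "lies entirely above 0.67". In protocol 9.4.3.1, non-inferiority "is demonstrated if the lower limit of the 2-sided 95% CI of the estimated GMR lies entirely above 0.67".

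The margin is stated five times with the fraction attached. Two are in the sample-size text (synopsis and protocol 9.2, which lists "a non-inferiority margin of 0.67 (2/3" in brackets among its assumptions). Three are in the sentence describing how the CI is used (synopsis, protocol 9.4.3.1 and SAP 5.3.2, where the back-transformed CI is "compared to the non-inferiority limits of 0.67 (2/3" in brackets).

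Protocol 9.2 continues: "A total of 105 evaluable participants per group are needed to have 90% power", and, after an allowance for exclusions, drop-outs and missing samples, "approximately 120 participants per group should be enrolled". SAP section 3 refers back to protocol 9.2. The layout of individual outputs "will be described in a separate data presentation specifications (DPS) document", which is not among the documents under review.

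**The concern.** This is the only pass/fail threshold in the study, and the two ways of writing it are not numerically equal. A lower limit between 0.6667 and 0.67 would miss the criterion as worded, yet clear the margin that appears to have been used for sizing. If limits were shown to two decimals (an assumption; the SAP does not say), such a limit would print as 0.67.

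No sentence says that 0.67 stands for 2/3 rounded, or that the unrounded limit is the one compared. By contrast, the SAP does fix a display precision for safety summaries: "Frequencies and percentages (one decimal place) will be generated for categorical variables". If the result landed in that narrow band, the verdict might seem to turn on a choice made after unblinding.

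**Working it through.** **Inputs** (protocol 9.2 unless noted): SD 1.3 on the log2 scale; true GMR 1; 2-sided alpha 5%, so 2.5% on the lower side; target power 90%; 105 evaluable and about 120 enrolled per group; 1:1 allocation (protocol 4.1); ANOVA with group as the only factor (protocol 9.4.3.1).

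**The two limits on the log2 scale**

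- log2(2/3) = -0.5850
- log2(0.67) = -0.5778

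**Reproducing the planned 105.** The normal approximation is n = 2 × [1.3 × (1.960 + 1.282) / d]², where d is the distance from 0 to the limit.

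- d = 0.5850: n = 103.8, so 104
- d = 0.5778: n = 106.4, so 107

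The exact calculation that matches the ANOVA uses the noncentral t with 2n - 2 degrees of freedom and noncentrality d / SE, where SE = 1.3 × √(2/n). At n = 105, SE = 0.1794, and the noncentrality is 3.260 for 2/3 and 3.220 for 0.67.

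| n per group | Power, limit 2/3 | Power, limit 0.67 |
|---|---|---|
| 104 | 89.79% | 89.06% |
| 105 | 90.07% | 89.35% |
| 107 | 90.60% | 89.90% |
| 108 | 90.85% | 90.17% |
| 120 | 93.47% | 92.90% |

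The smallest n reaching 90% is 105 with 2/3 and 108 with 0.67. The stated figure is therefore the exact t-based answer for 2/3. It is also close under the literal reading, at 0.65 points below 90%.

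**How often the readings disagree.** They disagree only when the lower limit falls between 0.6667 and 0.67. That probability is the difference between the two powers at a given true GMR.

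| True GMR | 105 per group | 120 per group |
|---|---|---|
| 1.00 | 0.7% | 0.6% |
| 0.95 | 1.1% | 1.0% |
| 0.90 | 1.5% | 1.4% |
| 0.85 | 1.6% | 1.7% |
| 0.80 | 1.4% | 1.6% |

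Over a grid of true GMRs from 0.6 to 1.2, the largest value is 1.6% with 105 per group and 1.7% with 120.

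**What it means for the estimate.** With 105 per group the CI half-width is 1.971 × 0.1794 = 0.3537 on the log2 scale. The smallest observed GMR that passes is 2^(-0.5850 + 0.3537) = 0.852 under 2/3, and 2^(-0.5778 + 0.3537) = 0.856 under 0.67.

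**Error rates.** If the margin is 2/3 and the literal 0.67 is applied, the one-sided error at a true GMR of 2/3 is 2.28%. If the margin is 0.67 and 2/3 is applied, the error at a true GMR of 0.67 is 2.74%. Each reading used consistently gives 2.50% at its own limit.

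**Scale.** With 2/3 held fixed, an SD of 1.25 instead of 1.35 moves the required n from 113 to 97. The margin reading moves it by 3.

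**The case for a change.** The strongest case for acting is that a primary decision rule should not need interpretation. All seven criterion statements omit the fraction, the literal reading is the stricter one, and a sponsor could argue for either value if the result fell in the band. One clear sentence would cost almost nothing, and leaving table layout to a separate specification does not replace a decision rule in the SAP.

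Part of this stands: no sentence in either document equates 0.67 with 2/3 or says that the unrounded limit is compared. That 2/3 is intended is an inference.

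It is a strong inference, however. In the synopsis, protocol 9.4.3.1 and SAP 5.3.2, the sentence immediately before the criterion gives the limit with the fraction. Only the hypothesis summaries (synopsis, protocol 3 and 9.1, SAP 2) lack that neighbour. The fraction is the one exact value the documents offer, it rounds to 0.67, and it reproduces the sample size. Nothing writes 0.670 or treats 2/3 as the approximation.

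The comparison with the safety section carries no weight, because a display format for descriptive percentages says nothing about a decision rule. The worry about a printed 0.67 also adds little: no text says the decision is taken on a rounded limit, and comparing the computed limit is ordinary practice.

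**Conclusion.** No change follows. The two notations are one margin written exactly and to two decimals, and a competent analyst would compare the unrounded lower limit with it. No stated figure is wrong: 105 per group gives 90.07% power with 2/3 and 89.35% with 0.67, and at 120 evaluable per group both readings give about 93%.

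The verdict would differ in 0.7% of trials at the planning assumption with 105 per group, and in at most about 1.7% at any true GMR with 105 or 120 per group. Whichever reading is followed, the conclusion is sound: the literal one is slightly conservative against a 2/3 margin (2.28% instead of 2.50%), and 2/3 keeps the planned 2.5% at the margin the sizing points to. Writing down the convention would tidy the text without changing the sample size, the analysis or the strength of the evidence.

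These figures assume the planning SD of 1.3, a common variance, normal log2 titers, and equal groups of 105 or 120 evaluable participants. That 2/3 was the sizing value is inferred from the match at 105.

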## 3. SAMPLE SIZE DETERMINATION

Refer to Section 9.2 of the CTP.

## 4. POPULATIONS (ANALYSIS SETS) FOR ANALYSIS

For vaccine studies, study intervention assignment will follow the as-treated principle.

**Table 2: Analysis Sets**

Analysis Set	Description
All Screened	
This analysis set includes all participants screened for the study, regardless if they were screen failures or they got enrolled in the study.
 
Rescreened participants are counted only once.

Full Analysis Set (FAS)	
The full analysis set (FAS) will include all participants who received study vaccination, regardless of the occurrence of protocol deviations and vaccine type (study vaccine or placebo).
 
All safety and participant information analyses will be based on the FAS.

Per Protocol Immunogenicity Analysis Set (PPI)	
The Per Protocol Immunogenicity Analysis Set will include all randomized participants who received study vaccine and for whom immunogenicity data are available. Samples taken after a participant experienced a major protocol deviation expected to impact the immunogenicity outcomes will be excluded from the PPI analysis.
 
The list of major protocol deviations that would lead to elimination from the immunogenicity analysis is specified in the major protocol violation criteria document, which will be finalized before database lock and unblinding.
 
The primary analysis set for analyses related to RSV immunogenicity is the PPI Set. As a sensitivity analysis, key tables may also be based on the FAS.

## 5. STATISTICAL ANALYSES

### 5.1. General Considerations

#### 5.1.1. Study Phases

A baseline (or reference) value will be defined as the value of the last available assessment prior to vaccination on Day 1. If there was no immunogenicity assessment done pre-vaccination, the assessment post-vaccination on Day 1 can be used as the baseline value for the immunogenicity analysis, if available.

The results of the safety analysis will be presented by phase. Immunogenicity results will be presented per scheduled time point as appropriate. Listings will be shown per phase and time point.

Study day or relative day is defined as follows:

- Study Day = visit date – date of Day 1 + 1; if visit date  $\geq$  date of Day 1 (date of vaccination).
- Study Day = visit date – date of Day 1; if visit date  $<$  date of Day 1 (date of vaccination).

### 5.1.2. Phase Definitions

The phases in the study will be constructed as follows:

**Table 3: Phase Definitions**

Phase	Phase #	Period	Period #	Interval	
				From	To
Screening	1			Date and time of signing the informed consent form	One minute prior to start of the Post-dose period
Regimen	2	Post-dose	1	Date and time of first vaccination	Minimum of: 
 
a) 23:59 at the date of last contact (for early discontinuation)
 
b) 23:59 at the database cut-off date for analyses conducted before the final analysis
 
c) maximum of (28 days after vaccination at 23:59, scheduled visit 28 days after vaccination at 23:59)
 

Follow-up	3			One minute after Post-dose period end	Minimum of: 
 
a) 23:59 at the date of last contact (for early discontinuation or participants that completed the study)
 
b) 23:59 at the database cut-off date for analyses conducted before the final analysis
 

The adverse events of special interest (AESI) analysis will be performed once by phase and once by time interval. The definition of the time intervals is shown in the table below. Additionally, in the tables a '0-56 days post-dose' interval and a '0-6 months post-dose' interval should also be shown. The '0-56 days post-dose' interval is the combination of the '0 - 28 days post-dose' interval and the '29 - 56 days post-dose' interval. The '0-6 months post-dose' interval is the combination of the '0 - 28 days post-dose', '29 - 56 days post-dose' and '57 days - 6 months post-dose' intervals.

**Table 4: Definition of intervals:**

Dose	Interval	From	To
Post-vaccination	0-28 days post dose	Date time of the 1st vaccination	Min of: 
 
• 23:59 at date of last contact (for discontinuations)
 
• 23:59 at date of DB cut-off for interim analyses
 
• Maximum(Date of Vaccination 2 + 28 days at 23:59, date of scheduled visit 4 weeks after 1st vaccination at 23:59 )
 

	29-56 days post dose	One minute after the end of the interval 0-28 days post dose	Min of: 
 
• 23:59 at date of last contact (for discontinuations)
 
• 23:59 at date of DB cut-off for interim analyses
 

			
 
• Date of Vaccination 1 + 56 days at 23:59
 

	57 days - 6 months post-dose	One minute after the end of the interval 29-56 days post dose	
Min of:
 
 
• 23:59 at date of last contact (for discontinuations)
 
• 23:59 at date of DB cut-off for interim analyses
 
• Date of Vaccination 1 + 183 days at 23:59
 

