## **6. STUDY VACCINE(S) AND CONCOMITANT THERAPY**

### **6.1. Study Vaccine Administration**

The investigational medicinal products (IMPs) to be administered to participants in this study are Ad26.RSV.preF and RSV preF protein.

The Ad26/protein preF RSV vaccine to be used in this study is composed of Ad26.RSV.preF and RSV preF protein, to be administered as a single injection (1.0 mL) in the deltoid muscle:

- Ad26.RSV.preF (JNJ-64400141) will be used at a dose level of  $1 \times 10^{11}$  vp.
- RSV preF protein (JNJ-64213175) will be used at a dose level of 150  $\mu\text{g}$ .

Ad26.RSV.preF and RSV preF protein will be manufactured and provided under the responsibility of the sponsor. Labels will contain information to meet the applicable regulatory requirements. Note that RSV preF protein CTM will be labelled as “RSV-F Vaccine”. Refer to the IB for Ad26/protein preF RSV vaccine for details of the components and a list of excipients ([IB Ad26/protein preF RSV vaccine 2021](#)).

Participants will be vaccinated at the study site according to the schedule shown in [Table 2](#). On Day 1, each participant will receive an IM injection of study vaccine (Ad26/protein preF RSV vaccine).

Study vaccine administration must be captured in the source documents and the electronic case report form (eCRF).

For a definition of study vaccine overdose, refer to Section [6.7](#).

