### Visit Windows

For the following visits, windows will be allowed as indicated:

Clinic Visit #	Visit Day	Visit Window	Primary Purpose
2	8	± 2 days	7 days after study vaccination, Safety visit, by telephone
3	15	± 3 days	14 days after study vaccination, Immunogenicity and Safety visit
4	29	± 5 days	28 days after study vaccination, Safety visit, by telephone
5	183	± 14 days	6 months after study vaccination, Safety visit, by telephone

The timings of the post-vaccination visits will be determined relative to the actual day of vaccination.

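### SAP Table 4 ends the 0–28 day AESI interval by the date of a second vaccination that no participant receives, so it does not match the Post-dose period in Table 3

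*SAP*

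**What the plan says.** Both documents describe a single vaccination. Protocol Section 6.1 states: "On Day 1, each participant will receive an IM injection of study vaccine". SAP Section 2 frames the comparison as "vaccination with one dose of the Phase 3 CTM compared with one dose of the Phase 2b CTM".

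SAP Section 5.1.2 defines two time structures for safety. In Table 3, item (c), the Post-dose period ends at the "maximum of (28 days after vaccination at 23:59, scheduled visit 28 days after vaccination at 23:59", subject to earlier last contact or data cut-off. Table 4 defines separate intervals for AESIs. The 0–28 day interval starts at the first vaccination and ends at the minimum of three terms: last contact (for discontinuations), database cut-off (for interim analyses), and "Maximum(Date of Vaccination 2 + 28 days at 23:59, date of scheduled visit 4 weeks after 1st vaccination".

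The 29–56 day interval starts "One minute after the end of the interval 0-28 days post dose" and its own third term is "Date of Vaccination 1 + 56 days at 23:59". The last interval runs to Vaccination 1 + 183 days.

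Both structures are used: the AESI "analysis will be performed once by phase and once by time interval". SAP Section 5.5.1.2 repeats this for all AESI analyses. It also treats the 0–28 day interval as the only active one when overlapping events are combined.

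**The concern.** The rule calls for a date that cannot exist in a one-dose trial. The other two rows of Table 4 use Vaccination 1, and Table 3(c), on the same page of logic, uses the only vaccination there is. The first row of Table 4 therefore cannot be a deliberate alternative; it looks like text carried over from a two-dose template, though that is an inference.

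At stake is agreement between two required sets of tables. The same AESI could appear within the first 28 days in the by-phase table and in the 29–56 day column of the by-interval table, because of a wrong vaccination number and not because of when it began. A function that skips missing values would return a plausible date with no error message, so the fault could pass unnoticed.

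**Working it through.** There is no stated figure to reproduce; the check is date logic.

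**Inputs**
- Vaccinations per participant: one, on Day 1 (Protocol 6.1; SAP 2). Count days from vaccination, so vaccination is +0.
- Visit 4, described in Protocol Section 8, Visit Windows, as "28 days after study vaccination, Safety visit, by telephone": Day 29 ± 5 days. Day 29 is +28, so the visit falls at v = +23 to +33, which is 11 permitted days.
- Table 3(c) end: max(28, v).
- Table 4 end as written: max(Vaccination 2 + 28, v), with Vaccination 2 missing.

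**Reading 1, missing value propagates.** The maximum is undefined for every participant. At the final analysis, for a participant who did not discontinue, neither other term applies, so the interval has no end.

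**Reading 2, missing value ignored.** The interval ends at 23:59 on the Visit 4 date, v. The shortfall against Table 3(c) is max(28, v) − v.

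| Visit 4 at | Table 3(c) end | Table 4 end | Shortfall (days) | Onset days that change interval |
|---|---|---|---|---|
| +23 | +28 | +23 | 5 | +24 to +28 |
| +24 | +28 | +24 | 4 | +25 to +28 |
| +25 | +28 | +25 | 3 | +26 to +28 |
| +26 | +28 | +26 | 2 | +27 to +28 |
| +27 | +28 | +27 | 1 | +28 |
| +28 to +33 | v | v | 0 | none |
| missed, not discontinued | +28 | none | undefined | undefined |

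The shortfall is non-zero on 5 of 11 days. If visits were spread evenly over the window (an assumption; the documents give no visit dates), the mean shift would be (5 + 4 + 3 + 2 + 1)/11 = 15/11 = 1.4 days. Without that assumption the range per participant is 0 to 5 days. These are shifts of the boundary, not rates of misallocated events.

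**Knock-on effects.** The 29–56 day interval starts one minute after the faulty end, so its start moves with it or is lost. The combination rules in SAP 5.5.1.3, Step 2, are also affected. Take Visit 4 at +23 and two overlapping events with the same preferred term, starting at +25 and +40. With the Table 3(c) boundary they straddle an active and a non-active interval, and rule 3 makes them one event in the active interval. With the Table 4 boundary both start in 29–56 days, and rule 2 makes them one event there.

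**What is not affected.** The ends at +56 and +183 days are anchored to Vaccination 1 and do not use the faulty term. The combined 0–56 day and 0–6 month intervals keep their outer limits. They are built by joining the component intervals, however, so they are safely computable only when the first component has an end.

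**The case against.** The strongest reply is that the intended rule can be recovered from the SAP itself. The row is labelled 0–28 days, starts at the first vaccination, pairs the faulty term with a visit counted from the first vaccination, and sits below a table that states the rule correctly. A careful programmer would correct it, and harm needs someone to code an impossible date without checking. This stands as a reason for low severity. It does not make the text right: this is an operative derivation rule, and the plan should not depend on a silent correction.

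Second, if the scheduled visit means the planned date (+28) and not the actual one, ignoring the missing term gives +28 for everyone and no shift. That reading is possible, but it would make the maximum pointless in both tables, so the actual date is the likelier meaning. The 0 to 5 day range includes zero in any case.

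Third, the 1.4-day average rests on an even spread of visits that nothing in the documents supports. That is so, and little weight should be put on it.

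Fourth, few events are likely to fall near the boundary. About 240 participants are planned, the safety tables carry no formal comparisons, and Protocol Section 2.2 places onset of thrombosis with thrombocytopenia at about 1 to 2 weeks. This also stands. However, the tables cover every potential AESI over 6 months, including myocardial infarction, stroke and pulmonary embolism (Protocol Appendix 6), and the documents do not confine those to the first two weeks.

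**Conclusion.** The point holds and is minor. Table 4 refers to a vaccination that does not occur and does not reproduce Table 3(c). Under the strict reading the bound is undefined for all participants. If the missing date is ignored and the actual Visit 4 date is used, the interval ends 1 to 5 days early on 5 of the 11 permitted visit days and has no end when Visit 4 was missed without discontinuation. The number of events that would change column may be nil. The effect is confined to the 28/29-day boundary in descriptive by-interval AESI tables and the event combination that uses it. The by-phase AESI tables, the primary non-inferiority test and the sample size are untouched.

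**What to change.** In SAP Table 4, first interval, third bullet, change Vaccination 2 to Vaccination 1 and keep the maximum. The bound becomes max(28, v). This equals Table 3(c) on all 11 permitted visit days, and stays at +28 if Visit 4 was missed by a participant still in follow-up. The 29–56 day interval then begins at the same moment as the Follow-up phase, with no gap or overlap. As in Table 3, the first interval will still run past +28 when Visit 4 takes place at +29 to +33, but the two presentations will agree.

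The cost is one digit in the SAP. No data, protocol text or Table 3 wording changes.
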